# Randomisation

The proportion of eligible participants willing to be randomised will be collected through the use of screening logs (Lancaster *et al.*, 2004). Participants will be randomly allocated to a control group or experimental group following the collection of baseline data. Block randomisation at a ratio of 1:1 will be used to ensure both groups comprise the same number of participants (Suresh, 2011). Patients will be randomly allocated according to the days of the week they attend the unit for haemodialysis, as opposed to at an individual level. As the renal unit is an open environment allocation according to shift pattern will reduce the risk of participants within the control group viewing implementation of the intervention, which would introduce potential contamination (Mc Daid *et al.*, 2006). Sealed envelopes will contain the allocation and these will be stored in a locked filing cabinet on site, and will be opened once consent and baseline data have been obtained. Participants who are randomly allocated to the control group will be instructed not to participate in any art activities during

their haemodialysis sessions throughout the study, but that once data collection is completed they will be provided with art supplies and participate in a facilitated session.

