#### Data analysis

Data analysis will be conducted using the Statistical Package for the Social Sciences (SPSS v 24). Descriptive statistics will be used to present baseline demographic and clinical data Categorical data will be presented as frequencies and percentages, while continuous data will be presented as means and standard deviations. Recruitment, participation and retention rates will be reported and presented in a CONSORT flow diagram (Eldridge *et al.*, 2016). The proportion of patients who were eligible for recruitment, who consented to participation and who completed the study will be calculated and presented with 95% confidence intervals. Exploratory inferential statistics will be conducted, but no conclusions on the effectiveness of the intervention will be made from the results. Independent t-tests (or the non-parametric equivalent Mann-Whitney U) will be conducted to compare the scores of the experimental group and control group. The majority of arts-based intervention research involves pre-and-

post-test designs; therefore a repeated measures t-test (or the non-parametric equivalent Wilcoxon Matched Pairs test) will also be conducted to compare the mean scores of the experimental before and after receiving the intervention. An analysis of variance will be conducted to explore any potential sub-group analysis that may be relevant within a future RCT.

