# Data analysis

A cost-consequence analysis is recommended by the National Institute of Health Research for both complex interventions and feasibility studies where the outcomes of interest are not clear (Hunter and Shearer, 2014). Costs and outcome measure data for both the intervention and control group will be presented using means and 95% confidence intervals in order to show a general overview of the economic costs of the intervention, and differences in resource use and outcome measures between groups. Completion rates and missing data for the Patient Service Use Log and the EQ-5D-5L will be presented as frequencies to assess the feasibility of data collection.

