Secondary quantitative outcomes: Chi squared tests will be conducted to establish whether the experimental and control group differ significantly in baseline demographic and clinical data. Completion of the KDQOL-SF36, HADS and EQ-5D-5L will be presented as proportions and rates. A cost consequence analysis will be used to provide a comparative overview of differences in costs and outcomes of participants in the experimental and control group.

Qualitative outcomes: The semi-structured interviews and focus groups will be recorded and transcribed verbatim. Inductive thematic analysis will be used to analyse the data collected. Investigator triangulation, method triangulation and data source triangulation will be used to ensure validity of the identified themes. A more comprehensive description of qualitative analysis is available in the study protocol.

Clinical outcomes: Exploratory inferential statistics will be conducted, but no conclusions on the effectiveness of the intervention will be made from the results. Independent t-tests (or the non-parametric equivalent Mann-Whitney U) will be conducted to compare the scores of the experimental group and control group. The majority of arts-based intervention research involves pre-and-post-test designs; therefore a repeated measures t-test (or the non-parametric equivalent Wilcoxon Matched Pairs test) will also be conducted to compare the mean scores of the experimental before and after receiving the intervention. An analysis of variance will be conducted to explore any potential sub-group analysis that may be relevant within a future RCT. The amount of time taken to conduct this analysis will be reported to inform feasibility.

6 Analysis details

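### Patients are allocated by dialysis days or shift, but the between-arm tests treat the 30 patients as individually randomised, and the shift structure is not stated

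*Protocol*

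**What the plan says.** **Allocation (Protocol, Phase 2, Randomisation).** Patients are "randomly allocated according to the days of the week they attend the unit for haemodialysis, as opposed to at an individual level". The reason given is to keep control patients in an open unit from seeing the intervention, and the section also describes this as allocation by shift pattern. The same section says "Block randomisation at a ratio of 1:1 will be used to ensure both groups comprise the same number of participants", and that the sealed envelopes "will be opened once consent and baseline data have been obtained".

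**Between-arm tests (Protocol, Phase 2, Data analysis; repeated in SAP section 5, Clinical outcomes).** "Independent t-tests (or the non-parametric equivalent Mann-Whitney U) will be conducted to compare the scores of the experimental group and control group".

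**Baseline tests (SAP section 5, Secondary quantitative outcomes).** "Chi squared tests will be conducted to establish whether the experimental and control group differ significantly in baseline demographic and clinical data".

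**Economic comparison (Protocol, Phase 4, Data analysis).** "Costs and outcome measure data for both the intervention and control group will be presented using means and 95% confidence intervals", partly to show differences between the groups.

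**Related analyses.** SAP section 5 adds: "An analysis of variance will be conducted to explore any potential sub-group analysis that may be relevant within a future RCT". A paired test "will also be conducted to compare the mean scores of the experimental before and after receiving the intervention" is also planned.

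**Safeguards.** Both documents call the clinical-outcome tests exploratory and rule out conclusions about effectiveness. The Progression Criteria depend on recruitment and acceptability.

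**The concern.** The unit allocated is a set of dialysis days or a shift; the unit analysed is the patient. Patients on one shift share staff, timing and each other's company, and may resemble each other in health or circumstances. If their scores are correlated for any such reason, a patient-level test understates the variance of the arm difference and its p-values are too small. If each arm is a single shift pattern, the arm difference is also a shift difference, and nothing in the data can tell them apart.

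The Randomisation section does not settle how the allocation works either. Blocking 1:1 at patient level and opening envelopes after consent and baseline read like individual randomisation; allocation by days does not. Two competent teams could run different trials from this text. Because one objective is to develop the protocol of the definitive trial, the study should show clearly whether it tested group allocation, and with how many groups.

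**Working it through.** **Plan's own figure.** There is none to reproduce. The 30 patients come from published guidance, not a power calculation, and the documents give no intracluster correlation (ICC), standard deviation or number of shifts.

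**Inputs.** From the documents: N = 30 at 1:1, so 15 per arm; allocation by days or shift; independent-sample tests. Assumed, not in the documents: 2, 3, 4 or 6 shifts in total; ICC 0 to 0.10; normal outcomes; no treatment effect.

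**Step 1. Closed form for two shifts (one per arm, 15 patients each).** Set the total variance to 1 and write ρ for the ICC.
- True variance of the difference in means: 2[ρ + (1 − ρ)/15].
- Variance that the t-test estimates, on average: 2(1 − ρ)/15, because it sees only variation within a shift.
- Ratio: 1 + 15ρ/(1 − ρ).
- True size of the nominal 5% test: 2 × P(T28 > 2.048/√ratio).

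| ICC | Ratio | 2.048/√ratio | True size |
|---|---|---|---|
| 0 | 1.000 | 2.048 | 5.0% |
| 0.01 | 1.152 | 1.909 | 6.7% |
| 0.05 | 1.789 | 1.531 | 13.7% |
| 0.10 | 2.667 | 1.254 | 22.0% |

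Solving for ρ, the size reaches 7.5% at ICC 0.015 and 10% at ICC 0.029.

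**Step 2. More shifts, by simulation (200,000 null trials per setting).** True size of the nominal 5% t-test:

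| Shifts (patients) | ICC 0.01 | ICC 0.05 | ICC 0.10 |
|---|---|---|---|
| 2 (15 v 15) | 6.6% | 13.7% | 22.0% |
| 3 (20 v 10) | 6.0% | 10.5% | 16.2% |
| 4 (8, 7 v 8, 7) | 5.7% | 9.0% | 13.2% |
| 6 (5 each) | 5.4% | 7.4% | 10.0% |

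At ICC 0 the size is about 5.0% throughout. Mann-Whitney U (40,000 trials) behaves similarly: 5.9%, 12.6%, 19.9% with 2 shifts and 5.1%, 6.5%, 8.9% with 6.

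**Step 3. Baseline chi-squared test (an item with 50% prevalence).** The result depends on the version, which the SAP does not name. With 2 shifts at ICC 0.01, 0.05 and 0.10:
- uncorrected: 5.6%, 10.2%, 16.1%;
- with continuity correction: 2.2%, 4.9%, 8.7%.

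With 4 or 6 shifts the corrected test stays below 5% over this ICC range.

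**Step 4. Can a shift-level analysis rescue the comparison?** Degrees of freedom are the number of shifts minus 2: 0, 2 and 4 for 2, 4 and 6 shifts. The critical t is then undefined, 4.30 and 2.78, against 2.05 on 28 df for the planned test. With one shift per arm there is no valid test at all.

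**Step 5. Equal numbers.** Suppose recruitment is not capped by shift and each recruit is equally likely to come from either arm's shifts (both assumptions). The arm size is then Binomial(30, 0.5): a 15:15 split has probability 0.144, and 18:12 or worse has probability 0.362. A cap for each shift pattern could secure equality, but none is stated.

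**The case against.** The strongest reply is that little rides on these tests. They are exploratory, effectiveness conclusions are ruled out, the primary Phase 2 outcome is recruitment and retention, and progression does not use them. That stands, and it sets the severity. It does not make the p-values correct, and neither document warns the reader about shift. In the SAP the no-conclusions statement also sits under Clinical outcomes, whereas the baseline chi-squared tests are listed separately.

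Second, the size rests on an ICC and a number of shifts that the documents do not give, and at the mild end (6 shifts, ICC 0.01) the inflation is negligible. This also stands, so the figures are a range and not an estimate. A reader might infer exactly two day patterns from the Phase 3 Recruitment section, which treats 48 hours as the time between sessions. That fits two patterns but does not establish them.

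Third, the fault might be thought to reach every inferential result. It does not:
- The pre-post test compares the experimental arm with itself, so a shift effect that is stable over time cancels; simulation gives about 5% at ICC 0.05 and 0.10.
- The analysis of variance is for exploring subgroups and its factors are not listed. Subgroup and interaction terms stay at 4% to 5% if subgroups are balanced over shifts; only an arm term, if one is fitted, inflates like the t-test.
- The confidence intervals in SAP section 6.4 are listed by service item, with no between-arm contrast named.

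Fourth, a lighter remedy would keep the tests and label them unadjusted for shift. That would warn the reader but leave p-values of unknown true size, and with one shift per arm they could not be interpreted. The protocol's Participants section criticises inappropriate hypothesis testing in pilot studies. That criticism is general and not about clustering, but it points the same way.

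**Conclusion.** The mismatch is real and follows from the documents' own words: allocation is by days or shift, the between-arm tests assume independently allocated patients, and no analysis text accounts for shift. Under the assumed 2 to 6 shifts and ICC 0.01 to 0.10, the nominal 5% t-test has a true size of about 5.4% to 22%; at ICC 0 it is valid. The effect on the baseline chi-squared tests is less certain because it depends on the continuity correction. With one shift pattern per arm, arm and shift are fully confounded.

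Severity is minor. A reader might infer that the sample size of 30 is wrong or that the feasibility conclusions are unsafe. Neither follows: 30 is not a power claim, and the progression decision does not use these tests. A reader might also infer that concealment fails. The text supports only a conditional statement: if envelopes are opened patient by patient, later recruits on an already allocated shift have a known arm. The information sheets and consent forms were not available, so what is described here as not stated refers to the remaining protocol and SAP text.

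**What to change.** 1. **Protocol, Randomisation.** Name the design as allocation by shift. State the number of shifts and whether each envelope covers a patient or a shift. Replace the promise of equal numbers with wording that blocking alone does not guarantee them. If envelopes are opened per patient, state that later recruits on an allocated shift will have a known arm.
2. **Protocol, Phase 2 Data analysis, and SAP section 5.** Replace the between-arm p-values and the baseline chi-squared tests with descriptive summaries by arm and by shift. Add: *If there is one shift per arm, the arm difference cannot be separated from a shift difference.* Attach the same caveat to any arm term in the analysis of variance. The subgroup terms and the experimental-arm pre-post test can stay as planned.
3. **Protocol, Phase 4 Data analysis.** Label any between-group comparison or 95% confidence interval as unadjusted for clustering by shift.

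**Cost.** Wording only: no extra patients, and no change to recruitment or envelope timing. The exploratory between-arm p-values are lost. The time taken for data analysis, which SAP sections 2.2 and 5 report as a feasibility outcome, would cover slightly less work.

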# **Data Collection and Management**

#### Feasibility measures

The main feasibility outcome of interest will be the recruitment, participation and retention rate of participants. Assessing the ability to recruit and retain participants is a common issue explored in feasibility trials (Lancaster *et al.*, 2004; Bugge *et al.*, 2013; Arain *et al.*, 2016; Avery *et al.*, 2017). As barriers to recruitment exist in palliative care research (Hanson *et al.*, 2015), and nephrology research commonly experiences high attrition rates (Palmer *et al.*, 2011), it is important to establish the feasibility of recruiting and retaining the participants needed for a definitive randomised controlled trial. Baseline demographic and clinical data will be include age, gender, ethnicity, socio-economic status, education, kidney diagnosis, dialysis vintage, number of co-morbidities and frailty as measured by the Clinical Frailty Scale; these will be collected to explore factors that may influence participation in a full trial.

#### Clinical outcome measures

Arts-based interventions can improve depression, a common issue in patients receiving haemodialysis (Bujang *et al.*, 2015). Improvements in depression have been reported in receptive arts groups; in a study by (Dowrick *et al.*, 2012) depression scores were measured in patients clinically diagnosed with depressive disorders using the PHQ-9, and a statistically significant reduction in depression was found after engagement in a reading group. Arts-based interventions have also been shown to impact anxiety, another common issue amongst patients receiving haemodialysis (Cohen *et al.*, 2016). As discussed earlier depression and anxiety are highly prevalent and under-addressed amongst patients with ESKD receiving haemodialysis, therefore depression and anxiety will be measured as a clinical outcome. These will be collected through the use of the Hospital Anxiety and Depression Scale (HADS), which has been validated in patients with ESKD (Loosman *et al.*, 2010). The scale measures depression and anxiety within the same tool, allowing independent exploration of two outcomes with a subscale analysis (Annunziata *et al.*, 2011).

Arts-based activities have also been found to contribute to QoL in clinical populations (Staricoff and Clift, 2011; Sturm *et al.*, 2014; Boyce *et al.*, 2017). As previously discussed patients receiving haemodialysis have lower HRQoL than the general population, and a

variety of factors contribute to this outcome. These include not only the physical symptoms patients experience, but psychological and social consequences of the disease and the associated treatments (Kang *et al.*, 2015). The Kidney Disease Quality of Life (KDQoL-36) is a commonly used measure of HRQoL in renal literature, is valid and reliable, and has been identified as providing the most comprehensive overview of factors that contribute to QoL (Glover *et al.*, 2011). Therefore the KDQoL-36 will be used to measure QoL.

The clinical outcome measures will be collected at baseline and immediately after the intervention. A pre/post-test design is common in arts-based intervention research and allows researchers to evaluate improvements in health outcomes over a short time period (Bungay *et al.*, 2014; Kim *et al.*, 2017). However, arts-based intervention research has faced criticism due to lack of longitudinal follow up, which would be necessary to identify whether arts-based interventions are sustainable in a clinical setting, and whether the benefits are lasting (Boyce *et al.*, 2017). Participants who are lost to follow up in longitudinal RCTs concerning complex healthcare interventions tend to be older, diagnosed with a chronic illness and have higher co-morbidity (Peterson *et al.*, 2012), common demographic factors in patients with ESKD (Zyoud *et al.*, 2016). To establish the feasibility of follow up within a definitive randomised controlled trial and establish attrition rates over time, a longitudinal follow up will also occur. This period will be limited by the time frame of the PhD programme, and clinical outcome measures will be collected pre and post intervention and at 6 weeks and 3 months after the intervention commences.

#### Data analysis

Data analysis will be conducted using the Statistical Package for the Social Sciences (SPSS v 24). Descriptive statistics will be used to present baseline demographic and clinical data Categorical data will be presented as frequencies and percentages, while continuous data will be presented as means and standard deviations. Recruitment, participation and retention rates will be reported and presented in a CONSORT flow diagram (Eldridge *et al.*, 2016). The proportion of patients who were eligible for recruitment, who consented to participation and who completed the study will be calculated and presented with 95% confidence intervals. Exploratory inferential statistics will be conducted, but no conclusions on the effectiveness of the intervention will be made from the results. Independent t-tests (or the non-parametric equivalent Mann-Whitney U) will be conducted to compare the scores of the experimental group and control group. The majority of arts-based intervention research involves pre-and-

post-test designs; therefore a repeated measures t-test (or the non-parametric equivalent Wilcoxon Matched Pairs test) will also be conducted to compare the mean scores of the experimental before and after receiving the intervention. An analysis of variance will be conducted to explore any potential sub-group analysis that may be relevant within a future RCT.

## **Phase 3 – Process evaluation**

# **Participants**

Participants will include both patients who have been recruited into phase 2 of the study, and healthcare staff working on the unit during the implementation of the intervention. Healthcare staff from the unit will also be recruited into the process evaluation.

Eligibility criteria for healthcare staff:

- A member of the multidisciplinary team, including nurses, healthcare support workers, doctors, dietitians, social workers and counsellors.
- Have had experience with the intervention.
- Have worked in a clinical renal setting for more than 3 months

Familiarity with the context of the clinical environment is needed to inform the acceptability of the intervention (May, 2013). Context includes the social system within in the work place, taking into consideration social norms, material resources, and collective commitment (May, 2013). A qualitative study by Farnell and Dawson (2006) interviewed critical care nurses over 6 months after transferring from general medical wards. Up to 3 months after commencing their new post nurses continued to report experiences relating to their socialisation, including the setting feeling 'so different', feeling deskilled in the new environment and being unable to meet the high expectations they set for themselves. At 6 months follow up these experiences were no longer reported. New staff and students require time to familiarise themselves with the clinical environment, the expectations involved in their role and the social structure of the unit (Valdez, 2008). Therefore healthcare staff who have worked in a renal setting for less than 3 months and students on placement during the intervention will be excluded from the evaluation.

# Recruitment

During data collection for phase 2 patients will be offered with the opportunity to participate in the process evaluation. A separate information sheet (Appendix 3) will be provided to interested participants by the researcher, participants will be given a minimum of 48 hours (time between dialysis sessions) to consider participation and a consent form (Appendix 4) will be provided for completion at the start of each interview.

Healthcare staff will be recruited for the process evaluation by purposive sampling. During the feasibility trial the ward manager, who will act as a gatekeeper, will approach healthcare staff and provide them with a participant information sheet containing contact details for the researcher (Appendix 5). Due to managerial and social hierarchies within hospitals healthcare, staff may feel pressure to participate; therefore the staff will be asked to contact the researcher if interested, so the gatekeeper will not be aware of who is participating.

# **Data Collection and Management**

Approximately 13 patients will be recruited into the process evaluation. Simulations have shown that this sample size of 10 should identify 80% of problems within a complex intervention (O'Cathain et al., 2014), while data saturation is likely to be reached at 12 interviews on average (Guest et al., 2006). The principle of 10 + 3 for data saturation outlines that a minimum of 10 interviews should be conducted, followed by at least 3 consecutive interviews that present no new findings (Francis et al., 2010), therefore a sample of 13 patients will be recruited for semi-structured interviews. Approximately 5 healthcare staff will be recruited into each focus group, with a proposed total of 3 focus groups (Schneider et al., 2009). The dialysis unit in which the study is taking place is relatively small, therefore the focus groups will be limited by the amount of staff available who meet the eligibility criteria and the requirement to produce a manageable amount of data for the time limitations of the study (Carlsen and Glenton, 2011; O'Cathain et al., 2014). However, these are approximate sample sizes, and data collection will continue until data saturation is reached. The researcher will provide the participants with a consent form prior to commencement of the focus group (Appendix 6). Data saturation will be determined when there is no new data being found from which additional themes can be developed (Guest et al., 2006).

Data collection for the process evaluation will occur in parallel to the feasibility randomised controlled trial, during implementation of the intervention and follow up (Moore *et al.*, 2014). The semi-structured interviews will be conducted with patients in their own home to maintain

confidentiality and avoid the power dynamic present in a clinical setting (Green and Thorogood, 2004). This approach will be flexible and patients can request that interviews occur during the haemodialysis session or on the unit if this is their preferred location. The focus groups with staff will take place in a private room on the haemodialysis unit. The process evaluation will follow the MRC guidance on process evaluations for complex evaluations (Moore *et al.*, 2014). It will therefore focus on the acceptability of the intervention, barriers and facilitators to implementation, the appropriateness of outcome measures, motivations for participation, reasons for continued engagement and potential mechanism of impact of the intervention.

The semi-structured interviews and focus groups will use interview guides consisting of open questions informed by the RE-AIM QuEST framework (Forman *et al.*, 2017). The interview guide will be flexible to ensure that participants can express and explore perspectives that they consider relevant to implementation, and will be reviewed by the advisory group and supervisory team who are responsible for providing objective oversight.

